8.3 Steps to Determine If an Adverse Event Requires Expedited Reporting

Step 1: Identify the type of adverse event

Step 2: Grade the adverse event

Step 3: Determine whether the adverse event is related to the protocol therapy

Attribution categories are as follows:

- Definite – The AE is clearly related to the study treatment.
- Probable – The AE is likely related to the study treatment.
- Possible – The AE may be related to the study treatment.
- Unrelated – The AE is clearly NOT related to the study treatment.

Note: This includes all events that occur within 30 days of the last dose of protocol treatment. Any event that occurs more than 30 days after the last dose of treatment and is attributed (possibly, probably, or definitely) to the agent(s) must also be reported accordingly.

Step 4: Determine the prior experience of the adverse event.

Expected events are those that have been previously identified as resulting from administration of the agent. An adverse event is considered unexpected, for expedited reporting purposes only, when either the type of event or the severity of the event is not listed in:

- The current known adverse events listed in the Agent Information Section of this protocol;
- The drug package insert;
- The current Investigator's Brochure

8.4 Reporting Requirements for Adverse Events/Unanticipated Problems Involving Risks to Subjects or Others

8.4.1 Expedited Reporting

- The Principal Investigator must be notified within 24 hours of learning of any serious adverse events, regardless of attribution, occurring during the study or within 30 days of the last administration of the study drug.
- The Cook Children's IRB must be notified of "any unanticipated problems involving risk to subjects or others" (UPIRTSO) as defined in Cook Children's Policy Number Cook Children's_HRPP_P08. UPIRTSOs, per HRPP policy P08 are considered to be those events that refer to any incident, experience, outcome or new information that: is unexpected, AND, Is related or possibly related to participation in the research, AND Indicates that subjects or others are at a greater risk of harm than was previously known or recognized, OR if a problem occurs with greater frequency, specificity, or severity than anticipated it should also be considered to be an unanticipated problem and should be reported to the IRB. UPIRTSOs are required to be reported to the IRB within 5 business days from the date that the PI determined the problem to be unanticipated using the Unanticipated Reportable Events Form in iMedRIS.
- All other adverse events - those that do not meet unanticipated problem criteria such as those that are expected, or are unlikely, or definitely not related, or those that are possibly related to the study participation - are not required to be reported to the IRB.

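### The list of events exempt from IRB reporting in section 8.4.1 names possibly related events, although the definition just above it counts them as qualifying

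*Protocol*

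**What the plan says.** The second bullet of Protocol 8.4.1 sets out when the IRB must be told of an unanticipated problem. Three conditions are joined by AND:

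- the event is unexpected;
- it meets the relatedness condition, "Is related or possibly related to participation in the research";
- it "Indicates that subjects or others are at a greater risk of harm than was previously known or recognized".

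An alternative route follows: a problem is also reportable "if a problem occurs with greater frequency, specificity, or severity than anticipated".

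The third bullet says which adverse events need not go to the IRB. It describes them as "those that do not meet unanticipated problem criteria such as those that are expected, or are unlikely, or definitely not related", and then adds one more example: "or those that are possibly related to the study participation".

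Section 8.3 supplies the attribution scale. It has four categories: definite, probable, possible and unrelated. The third reads "Possible – The AE may be related to the study treatment". A note in the same section says that an event arising more than 30 days after the last treatment and "attributed (possibly, probably, or definitely) to the agent(s) must also be reported accordingly".

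**The concern.** Two adjacent bullets use the same attribute in opposite ways. In the first, possible relation helps to make an event reportable. In the second, it is offered as an illustration of an event that is not. A person deciding under a deadline is likely to look at the worked examples, and here an example points the wrong way.

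What is at stake is the flow of safety information to the IRB while children are still being treated. Section 1.3 states that studies of 6-Hz primed high-frequency stimulation of the ipsilesional hemisphere in cerebral palsy are notably absent. With so little prior experience, possible is a plausible attribution for an unexpected event, and an event of that kind that signals greater risk is what the definition is meant to bring to the IRB.

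**Working it through.** No arithmetic applies. The check sets the definition beside the exempt list and runs the attribution categories and event types through both.

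**Step 1: relatedness alone, by the four categories of 8.3.**

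| Attribution | Relatedness condition in the definition | Exempt example in the next bullet |
|---|---|---|
| Definite | met | not named |
| Probable | met | not named |
| Possible | met | named as exempt |
| Unrelated | not met | named as exempt |

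The two bullets agree on three categories and disagree on one, possible. If the examples were used as a filter, the relatedness condition would shrink to definite and probable only.

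**Step 2: possibly related events, by the other conditions.**

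- (a) Unexpected and indicating greater risk. All three conditions are met, so the definition makes it reportable. The example suggests it is exempt. Conflict.
- (b) Unexpected, no indication of greater risk, not in excess of what was anticipated. The definition does not make it reportable. No conflict.
- (c) Expected, and not in excess. The definition does not make it reportable, and the exempt list already covers it as expected. No conflict, and the disputed phrase is not needed.
- (d) More frequent or more severe than anticipated. The alternative route makes it reportable without reference to attribution. The example again points the other way.

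The disputed phrase therefore does no useful work in (b) or (c), and it misleads in (a) and (d).

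**Step 3: comparison with 8.3.** The note on late events puts possible together with probable and definite on the reportable side. It does not name the IRB as recipient, so it does not settle the question alone, but it shows that the protocol elsewhere treats possible relation as a reason to report.

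**Step 4: after deleting the phrase.** (a) and (d) are reportable with no contrary example. (b) stays exempt because it fails the greater-risk condition, and (c) stays exempt as expected. No legitimate exemption is lost.

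**The case against.** The strongest reply is that the exemption does not stand alone. It applies only to events that have already failed the definition, and its examples are illustrations. On that reading the phrase means only that possible relation by itself does not make an event reportable, which is true, because the definition also asks for unexpectedness and greater risk. This stands as a matter of strict construction. A reader might infer that the protocol formally waives IRB reporting of all possibly related events; the text does not support that. The reply does not rescue the wording, however. The neighbouring examples (expected, unlikely, not related) are each offered as a reason for failing the criteria, and possible relation is no such reason.

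A second reply is that other routes remain. Serious adverse events must reach the principal investigator within 24 hours whatever the attribution, and excess frequency, specificity or severity is a separate ground for IRB reporting. Both are correct. The first brings the event to the investigator, though, not to the IRB, and the investigator's decision to go further then rests on the two conflicting bullets.

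A reader might also infer that a possibly related seizure would go unreported. That goes too far. Sections 3.2.2 and 7.1.1 list seizure as a known risk of the technique, so it may be exempt as expected whatever the disputed phrase says, and 8.2.3 gives convulsions without hospitalization as an example of what may be considered for reporting as serious. Whether a seizure counts as expected is a separate uncertainty, since 8.3 refers to an agent information section that does not appear under that name in the table of contents.

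Finally, 8.4.1 takes its definition from an institutional policy that is not at hand. Actual under-reporting therefore cannot be shown from the protocol.

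**Conclusion.** The contradiction is real and sits in an operative safety rule: 8.4.1 names possibly related events as exempt although its own definition counts them as qualifying, and 8.3 leans the same way as the definition. The supported consequence is limited. Someone who relies on the example could misclassify an unexpected, possibly related event that indicates greater risk as not reportable to the IRB. It is not a formal waiver, and it does not affect the 24-hour notice of serious adverse events to the principal investigator.

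The conflict concerns one of four attribution categories. No number of affected events can be given. The seizure rates in 7.1.1 are for patients without a neurologic condition and for patients with epilepsy; neither describes this population, from which a history of epilepsy is excluded (4.2.4). Sample size, power, type I error and the analysis are not touched. The conclusion assumes that the protocol's paraphrase of the institutional policy is the text that staff will work from. The point deserves correction because it is a reporting rule in a paediatric trial and the repair is trivial.

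**What to change.** In 8.4.1, delete "or those that are possibly related to the study participation" from the examples of events that need not go to the IRB, so that the list agrees with the definition above it. If the phrase was a slip for its negative, it still has to be corrected, and deletion achieves the same result. While the sentence is open, it could be aligned with the four categories in 8.3, since the term for unlikely events is not one of them.

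The cost is one phrase in the next amendment and, in use, at most a few more IRB reports. Possibly related events that are expected and not in excess remain exempt.

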9. INTERVENTION DISCONTINUATION

9.1 Removal of Patients from Protocol Therapy

Patients can be taken off the study treatment and/or study at any time at their own request, or they may be withdrawn at the discretion of the investigator for safety, behavioral or administrative reasons. The PI will be notified and the reason(s) for discontinuation, as well as the date patient was removed from study, will be documented and may include:

- 9.1.1 Patient voluntarily withdraws from treatment (follow-up permitted);
- 9.1.2 Patient withdraws consent (termination of treatment and follow-up);
- 9.1.3 Patient is unable to comply with protocol requirements;
- 9.1.4 Patient demonstrates disease progression (unless continued treatment with study drug is deemed appropriate at the discretion of the investigator);
- 9.1.5 Patient experiences toxicity that makes continuation in the protocol unsafe;
- 9.1.6 Treating physician judges continuation on the study would not be in the patient's best interest;
- 9.1.7 Patient becomes pregnant (pregnancy to be reported along same timelines as a serious adverse event);
- 9.1.8 Lost to follow-up. Example language: If a research subject cannot be located to document survival after a period of 2 years, the subject may be considered "lost to follow-up." All attempts to contact the subject during the two years must be documented and approved by the Data Monitoring Committee.

9.2 Subject Withdrawals or Discontinuation of Study Intervention

Patients can withdraw from the study at any request or at the investigator's discretion for administrative, behavioral, or safety concerns. The patient will be taken out of the study on the day that the principal investigator is informed, and the reason(s) for stopping will be recorded, perhaps including:

- a. The patient gives up willingly;
- b. The patient is not able to follow the regimen;
- c. The treating physician determines that continuing the research would not be in the patient's best interest.

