10. STATISTICAL CONSIDERATIONS

Sample Size and Power Analysis: We will estimate the signal-to-noise ratio (SNR) at the sensor level, which will allow us to calculate the intra-subject variability. Given this SNR, we anticipate an effect size (Cohen's *d*) of greater than 0.5 in the primary motor cortex (M1). For an effect size of 0.5, 15 subjects per group are required to achieve 80% power at a significance level of 0.05. This estimation assumes a moderate effect of 6-Hz primed rTMS on motor function and meta-plasticity outcomes.

Handling Missing Data: Given the possibility of dropouts or incomplete data, particularly in a pediatric population, multiple imputation methods will be employed to handle missing data. We will also conduct sensitivity analyses to assess the impact of missing data on the results, ensuring robustness in our findings.

Multiple Comparisons and Adjustment: Considering the multiple outcome measures related to motor function, cortical excitability, and meta-plasticity, we will apply False Discovery Rate (FDR) adjustments to control for Type I error. This approach balances the need to maintain statistical rigor while not being overly conservative, which is crucial given the exploratory nature of some of our outcomes.

Effect Size and Clinical Relevance: While statistical significance will be assessed using *p*-values, we will also report effect sizes (Cohen's *d*) to gauge the practical relevance of our findings. An effect size greater than 0.5, particularly in motor outcomes, will be considered clinically meaningful, contributing to the broader understanding of rTMS effects in pediatric CP.

Controlling for Confounding Variables: Behavioral scores, laterality, age, and gender will be included as covariates in our analysis to control for their potential confounding effects. We will employ Analysis of Covariance (ANCOVA) models to adjust for these variables, ensuring that the observed effects are attributable to the rTMS intervention rather than these extraneous factors.

Longitudinal Data Analysis: Given the repeated measures design, where participants will be assessed at multiple time points, we will use mixed-effects models to account for within-subject correlations. This approach will allow us to capture the temporal dynamics of rTMS effects on motor function and meta-plasticity accurately, providing a more comprehensive understanding of the intervention's impact over time.

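### Section 9.2 merges stopping the sessions with leaving the study, conflicts with section 9.1, and so risks avoidable missing outcomes in arms of 15

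*Protocol*

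**What the plan says.** Protocol section 9.2 carries a heading that names both subject withdrawal and discontinuation of the study intervention. Its text has one consequence for all cases: "The patient will be taken out of the study on the day that the principal investigator is informed". The reasons it lists include "The patient is not able to follow the regimen". It says nothing about assessments after that day.

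Protocol section 9.1 deals with removal from protocol therapy and treats the two events as separable: "Patients can be taken off the study treatment and/or study at any time at their own request". Three of its listed reasons matter here:

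- 9.1.1: "Patient voluntarily withdraws from treatment (follow-up permitted", so stopping treatment does not by itself end data collection.
- 9.1.2: "Patient withdraws consent (termination of treatment and follow-up", the only reason that expressly ends follow-up.
- 9.1.3: "Patient is unable to comply with protocol requirements", with no word on follow-up.

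Protocol section 10 (Statistical Considerations) expects dropout and says that "multiple imputation methods will be employed to handle missing data". It adds: "We will also conduct sensitivity analyses to assess the impact of missing data on the results". Mixed-effects models are planned for the repeated measures.

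**The concern.** Inability to comply appears in both sections. Section 9.1.3 is silent on follow-up, so 9.2 is the only text that tells staff what happens next, and it says that the child leaves the study. Under section 3.1, behavioural assessment takes place at baseline, after the intervention, and at follow-up within one month. A child removed during the session period therefore has a baseline GMFM-88 and none afterwards. That child also has no post-intervention or 1-month TEP, although EEG recorded during completed sessions may exist.

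The loss could depend on arm. Section 3.6.4 has the sham coil perpendicular to the scalp with no active stimulation, and section 7.1.1 puts headache or neck pain at up to 20 in 100 TMS patients. Stopping driven by tolerability could then be more common in the active arms. This is plausible, but the protocol gives no figure for it.

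At stake is the randomised comparison on both primary outcomes. With 15 children per arm, a few selective removals matter. A statistical analysis plan can choose how to handle missing visits, but it cannot recover visits that the protocol told staff not to hold.

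**Working it through.** **Step 1. The two sections side by side.**

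| Situation | Section 9.1 | Section 9.2 |
|---|---|---|
| Child chooses to stop sessions | Follow-up permitted (9.1.1) | Out of the study that day, if voluntary stopping is read to include stopping sessions |
| Child cannot follow the regimen | Removal; silent on follow-up (9.1.3) | Out of the study that day |
| Physician judges that continuing is not in the child's interest | Removal; silent on follow-up (9.1.6) | Out of the study that day |
| Consent withdrawn | Treatment and follow-up end (9.1.2) | Not listed separately |

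The first row is a conflict on that reading. In the second and third rows, 9.2 fills a gap in 9.1 by ending participation.

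**Step 2. The plan's own figures.** Section 10 gives d = 0.5, 15 per group, 80% power and alpha 0.05, and section 10.1.1 makes tests two-tailed. A two-sample t-test with these inputs needs 64 per arm, and 15 per arm gives 26.2% power. The stated 15 does not reproduce. That is a separate sample-size matter; here 26.2% serves only as the starting point for the power loss.

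**Step 3. Shift in an arm's observed mean.** Suppose k of 15 children are removed from one arm and would have scored D standard deviations below its completers.

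- Mean of all randomised = completer mean − (k/15) × D.
- Shift = (k/15) × D.

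The protocol gives neither k nor D. Assumed ranges: k = 1 to 4, D = 0.5 to 1.0 SD.

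| k removed | Shift at D = 0.5 | Shift at D = 1.0 | Power at d = 0.5 if k are lost from **both** arms |
|---|---|---|---|
| 0 | 0 | 0 | 26.2% |
| 1 | 0.033 | 0.067 | 24.7% |
| 2 | 0.067 | 0.133 | 23.2% |
| 3 | 0.100 | 0.200 | 21.6% |
| 4 | 0.133 | 0.267 | 20.1% |

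The extremes are (1/15) × 0.5 = 0.033 SD and (4/15) × 1.0 = 0.267 SD, which are 7% and 53% of the design d of 0.5 (0.033/0.5 and 0.267/0.5).

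**Step 4. When both arms lose children.** With the same D in each arm, the shift in the between-arm difference is ((k₁ − k₂)/15) × D. For 3 against 1 it is (2/15) × 0.5 to (2/15) × 1.0, or 0.07 to 0.13 SD. Equal losses with equal D cancel. The sign reverses if the removed children would have done better than completers.

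**Step 5. What these figures describe.** They are shifts in an unadjusted observed-completer mean, before imputation, covariate adjustment or a mixed model. They are not the bias of the planned analysis. The shift and power columns are also separate scenarios: the shift supposes loss in one arm, the power column equal loss in both.

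**The case against.** A reader might infer that the sham comparison turns into a comparison of completers. The protocol does not support that. Nothing restricts the analysis to completers, and section 10 plans multiple imputation, mixed-effects models and missing-data sensitivity analyses. Nor does section 10 tie the imputation to a missing-at-random assumption; that detail may sit in a statistical analysis plan that is not at hand.

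A reader might also infer that no outcome is ever observed after a child stops. Section 9.1.1 contradicts this for children who choose to stop treatment. There is a coherent reading in which 9.1 governs stopping treatment and 9.2 governs leaving the study, since the body of 9.2 opens with withdrawal from the study.

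Both objections limit the point without removing it. The heading of 9.2 names discontinuation of the intervention and its reasons include regimen non-adherence, so staff could fairly apply it to a child who only stops sessions. Imputation keeps such a child in the analysis, but if 9.2 is followed the trial holds no off-treatment outcomes against which to check the imputed ones. Sensitivity analyses can show how much the answer depends on the assumption; they cannot supply the missing observations.

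A further objection concerns the remedy. TEPs and MEPs require TMS pulses, so keeping every child in all assessments would bring children stopped for safety, or on a physician's judgement, back to stimulation. That objection stands, and it limits the fix.

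**Conclusion.** The point holds as a conflict between sections 9.1 and 9.2 whose likely result is avoidable, possibly arm-related missing data at the post-intervention and 1-month visits. The planned methods would retain the affected children, but would rest on assumptions about off-treatment outcomes that the trial's own data could not check.

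The size cannot be fixed from the protocol, which gives no dropout rate, no difference between arms and no outcome difference for children who stop. Under the assumed ranges, one arm's observed-completer mean moves by about 0.03 to 0.27 SD against a design d of 0.5. The added power loss is small: from 26.2% to 20.1% even if 4 of 15 are lost from both arms. The main harm is selective loss of outcomes. Given the low cost of correction, the wording should be changed.

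**What to change.** Amend section 9.2 to agree with section 9.1:

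1. Define stopping the sessions and leaving the study as separate events.
2. State that a child who stops sessions but has not withdrawn consent is still offered the planned post-intervention and 1-month outcome assessments, at least the behavioural ones such as GMFM-88, and is kept in the assigned arm.
3. Fill the silence on follow-up in 9.1.3 in the same terms.
4. Reserve multiple imputation for visits that could not be obtained.

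Whether TMS-based assessments (TEPs, MEPs) continue for children stopped for safety or on physician judgement is a clinical matter. The sponsor must reconcile 9.1.5, 9.1.6 and 9.2(c) on it, and this review proposes no rule. When a child should stop treatment is likewise not touched.

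The cost is amendment wording, plus assessment visits already in the schedule for the few children who stop early. The planned sample size does not change.

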9.3 Premature Termination or Suspension of Study

This study may be suspended or prematurely terminated if there is sufficient reasonable cause. Written notification, documenting the reason for study suspension

or termination, will be provided by the suspending or terminating party to the PI, DSMB, funding agency, the Investigational New Drug (IND) /Investigational Device Exemption (IDE) sponsor and regulatory authorities. If the study is prematurely terminated or suspended, the PI will promptly inform the IRB and will provide the reason(s) for the termination or suspension.

Circumstances that may warrant termination include, but are not limited to:

- Determination of unexpected, significant, or unacceptable risk to subjects.
- Insufficient adherence to protocol requirements.
- Data that are not sufficiently complete and/or evaluable.
- Determination of futility.

